Grade 4	Mandatory: Permanently discontinue patient from treatment
Investigations (renal)	
Serum creatinine	
Grade 1 (> ULN - 1.5 x ULN)	Recommendation: Maintain dose level
Grade 2 (> 1.5 - 3.0 x ULN)	Recommendation: Hold dose until resolved to grade ≤ 1 or baseline, then maintain dose level
Grade 3 (> 3.0 - 6.0 x ULN)	Mandatory: Permanently discontinue patient from treatment
Grade 4 (> 6.0 x ULN)	Mandatory: Permanently discontinue patient from treatment
Investigations (hepatic)	
Isolated total bilirubin elevation	
> ULN – 1.5 x ULN, if baseline was normal	Recommendation: Maintain dose level
> 1.5 - 3.0 x ULN if baseline was normal	Recommendation: Maintain dose. Repeat Liver Function Tests (LFT) within 48-72 hours then monitor LFTs ^b weekly, or more frequently if clinically indicated, until resolved to ≤ 1.5 x ULN or baseline: if resolved in ≤ 14 days, then maintain dose level if resolved in > 14 days, then reduce dose ↓ 1 dose level
> 3.0 - 10.0 x ULN (irrespective of the baseline levels) *	Mandatory: Hold dose. Repeat LFTs within 48-72 hours then monitor LFTs ^b weekly, or more frequently if clinically indicated, until resolved to ≤ 1.5 x ULN or baseline: if resolved in ≤ 14 days, then reduce dose ↓ 1 dose level if resolved in > 14 days, then discontinue patient from treatment.

Dose modifications for asciminib	
Please note that if a patient requires a dose interruption of > 28 days for any toxicity, and > 42 days for hematologic toxicity, then the patient should be discontinued from study treatment	
Worst toxicity CTCAE Version 5.0	Asciminib
	The patient should be monitored weekly (including LFTs ^b), or more frequently if clinically indicated, until total bilirubin level has resolved to baseline or has stabilized over 4 weeks
> 10.0 x ULN (irrespective of the baseline levels) *	See footnote**** - otherwise discontinue study treatment The patient should be monitored weekly (including LFTs ^b), or more frequently if clinically indicated, until total bilirubin level has resolved to baseline or has stabilized over 4 weeks
Isolated AST or Alanine Aminotransferase (ALT) elevation	
If normal at baseline:	
> ULN - 3.0 x ULN	Recommendation: Maintain dose level Repeat liver tests within 48- 72 hours, then monitor weekly until recovery to ≤Grade 1 or to baseline

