> 3.0 - 5.0 x ULN	Recommendation: Maintain dose level. Repeat LFTs ^b as soon as possible, preferably within 48-72 hours from awareness of the abnormal results; if abnormal lab values are confirmed upon the repeat test, then monitor LFTs ^b weekly, or more frequently if clinically indicated, until resolved to ≤ 3.0 x ULN
> 5.0 - 10.0 x ULN	Mandatory: Omit dose. Repeat LFTs ^b as soon as possible, preferably within 48-72 hours from awareness of the abnormal results; monitor LFTs ^b weekly, or more frequently if clinically indicated, until resolved to ≤ 3.0 x ULN. Then: If resolved in ≤ 14 days, resume at prior dose level If resolved in > 14 days, resume with reduced dose ↓ 1 dose level
> 10.0 - 20.0 x ULN	Mandatory: Omit dose. Repeat LFTs ^b as soon as possible, preferably within 48-72 hours from awareness of the abnormal results; monitor LFTs ^b weekly, or more frequently if clinically indicated, until resolved to ≤ baseline. Then resume with reduced dose ↓ 1 dose level
> 20.0 x ULN	Mandatory: Permanently discontinue
If elevated at baseline:	
> Baseline - 3.0 x Baseline AND ≤ 5 x ULN	Recommendation: Maintain dose level
> 3.0 x Baseline AND > 5.0 x ULN (duration less than 2 weeks)	Recommendation: Maintain dose level. Repeat LFTs ^b as soon as possible, preferably within 48-72 hours from awareness of the abnormal results; if abnormal lab values are confirmed upon the repeat test, then monitor LFTs ^b weekly, or more frequently if clinically indicated, until resolved to ≤ ULN or baseline
> 3.0 x Baseline AND > 5.0 x ULN (duration more than 2 weeks):	Mandatory: Omit dose. Repeat LFTs ^b as soon as possible, preferably within 48-72 hours from awareness of the abnormal results; if abnormal lab values are confirmed upon the repeat test, then monitor LFTs ^b weekly, or more frequently if clinically indicated, until resolved to ≤ ULN or baseline. If resolved, resume with reduced ↓ 1 dose level.
> 5.0 x Baseline AND > 8.0 x ULN (irrespective of the duration):	Mandatory: Omit dose. Repeat LFTs ^b as soon as possible, preferably within 48-72 hours from awareness of the abnormal results; if abnormal lab values are confirmed upon the repeat test, then monitor LFTs ^b weekly, or more frequently if clinically indicated, until resolved to ≤ ULN or baseline. If resolved, resume with reduced ↓ 1 dose level.
> 20.0 x ULN	Permanently discontinue
Combined ^c elevations of AST or ALT and total bilirubin	

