
Systolic BP 140-159 mm Hg or Diastolic BP 90-99 mm Hg
	
Mandatory: If recurrent or persistent (≥24 hrs), or if symptomatic increase by >20 mm Hg (diastolic) or to >140/90 mm Hg; monotherapy anti-hypertensive treatment indicated; Maintain asciminib dose level, with regular monitoring of blood pressure.

Systolic BP ≥160 mm Hg or Diastolic BP ≥100 mm Hg
	
Medical intervention indicated: Initiate antihypertensive therapy (if not currently being treated with antihypertensive). If already taking anti-hypertensive drugs; intensive treatment with increased dose of existing anti-hypertensive/ more than one anti-hypertensive drugs than previously used Hold asciminib dose until resolved to grade ≤ 2, then reduce dose ↓ 1 dose level

CTCAE Grade 4
	
Mandatory: Permanently discontinue patient from treatment

Gastrointestinal
	

Pancreatitis
	

Dose modifications for asciminib	
Please note that if a patient requires a dose interruption of > 28 days for any toxicity, and > 42 days for hematologic toxicity, then the patient should be discontinued from study treatment	
Worst toxicity CTCAE Version 5.0	Asciminib
Grade 2 (radiologic findings for pancreatitis as per CTCAE v5.0, for increased enzymes please see table for asymptomatic amylase and/or lipase elevation)	Mandatory: If asymptomatic radiologic pancreatitis, hold treatment until recovery of the radiologic findings. If treatment delay is ≤ 21 days, then reduce dose ↓ 1 dose level. If treatment delay > 21 days, discontinue treatment and keep monitoring with appropriate imaging (i.e., MRI, CT scan, or ultrasound) **
Grade ≥ 3	Mandatory: Permanently discontinue patient from treatment. Obtain appropriate imaging (i.e., MRI, CT scan, or ultrasound)
Diarrhea***	
Grade 1	Recommendation: Maintain dose level but initiate anti-diarrhea treatment
Grade 2	Recommendation: Hold dose until resolved to grade ≤ 1, then maintain dose level If diarrhea returns as grade ≥ 2, hold dose until resolved to grade ≤ 1, then reduce dose ↓ 1 dose level
Grade 3	Recommendation: Hold dose and discontinue patient from treatment
Grade 4	Mandatory: Permanently discontinue patient from treatment
Skin and subcutaneous tissue disorders	
Rash/photosensitivity	
Grade 1	Recommendation: Maintain dose level. Consider initiating appropriate skin toxicity therapy (such as antihistamines, topical corticosteroids and low-dose systemic corticosteroids)

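### Table 6-4: the diarrhea recurrence sentence overlaps the Grade 3 and Grade 4 rows, and the mild-bilirubin row reduces the dose only after late resolution and gives no further instruction for a value that stays raised

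*Protocol*

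**What the plan says.** Both rows are in Protocol Section 6.6.3, Table 6-4.

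**Diarrhea.** The Grade 2 row is a recommendation: hold until grade 1 or lower, then keep the dose level. It then adds a recurrence sentence: "If diarrhea returns as grade ≥ 2, hold dose until resolved to grade ≤ 1, then reduce dose ↓ 1 dose level". The Grade 3 row reads "Recommendation: Hold dose and discontinue patient from treatment". The Grade 4 row is labelled Mandatory and calls for permanent discontinuation.

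**Isolated total bilirubin.** The row headed "> 1.5 - 3.0 x ULN if baseline was normal" starts "Recommendation: Maintain dose. Repeat Liver Function Tests (LFT) within 48-72 hours then monitor LFTs". Monitoring runs weekly, or more often, until the value is back to 1.5 x ULN or baseline. Two branches follow: "if resolved in ≤ 14 days, then maintain dose level" and "if resolved in > 14 days, then reduce dose ↓ 1 dose level".

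**Analysis.** SAP 2.5.3 counts treatment discontinuation before Week 48 for any reason as non-response. Dose modification and interruption are handled by treatment policy, so the observed Week 48 value counts.

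**The concern.** A dose-modification table should give one action for each patient state. In the diarrhea rows, a patient whose earlier Grade 2 episode resolved and who now has Grade 3 diarrhea falls under two instructions, one leading to a lower dose and the other to stopping. Two sites could each follow the table and treat identical patients differently. Before Week 48, they would also send them down different paths in the primary analysis.

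In the bilirubin row, the only trigger for a reduction is that the value has already resolved, late, while the patient stayed on the same dose. The patient whose value has not come down gets no instruction beyond maintaining the dose and monitoring. That order is odd for a safety rule, and it leaves the persistent case to each investigator.

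**Working it through.** No sample-size, power or alpha figure is involved, so the check is a side-by-side reading of the rows.

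**Diarrhea, after a Grade 2 episode that resolved and was resumed at the same dose**

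| Grade at return | Recurrence sentence (Grade 2 row, Recommendation) | Row for the grade reached | Result |
|---|---|---|---|
| 2 | hold, then one level lower | same row | one instruction |
| 3 | hold, then one level lower | hold and discontinue (Recommendation) | two instructions |
| 4 | hold, then one level lower | permanently discontinue (Mandatory) | two instructions, different labels |

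Four pieces of text might break the tie:

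1. *The labels.* A mandatory action ordinarily outranks a recommendation, which arguably decides Grade 4. At Grade 3 both rows are recommendations, so the labels do not help.
2. *The footnote tying modifications to the worst preceding toxicity.* It may point to the row for the grade reached, but it does not mention the recurrence sentence, which itself covers grade 2 and above.
3. *The rule in Section 6.6.3 that a patient stops if a toxicity recurs at the same or worse severity.* It applies after resumption at a lower dose level. Here the first episode was resumed at the same level.
4. *Section 9.1.1.* For recurring adverse events it only refers back to Table 6-4.

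Grade 3 therefore stays unsettled.

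**Bilirubin above 1.5 and up to 3.0 x ULN, normal baseline**

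| State | Action in the row |
|---|---|
| Still in this range, any duration | maintain dose, monitor; nothing further |
| Resolved within 14 days | maintain dose level |
| Resolved after more than 14 days | reduce one level |

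No state receives two actions. Read literally, though, a value that resolves on day 15 triggers a reduction, while one still raised on day 30 does not. The table's 28-day limit does not catch the second patient, because it counts interruption and this row has none.

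The table uses two other patterns for duration, and this row fits neither:

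- *Hold, then count.* The Grade 3 and 4 neutropenia and thrombocytopenia rows, bilirubin above 3.0 and up to 10.0 x ULN, Grade 3 amylase or lipase, and AST/ALT above 5.0 and up to 10.0 x ULN first stop the drug and then act on the time to resolution. The last of these says "If resolved in > 14 days, resume with reduced dose ↓ 1 dose level".
- *Act on persistence.* For AST/ALT elevated at baseline (above 3.0 x baseline and above 5.0 x ULN), the dose is maintained if the elevation has lasted less than 2 weeks and omitted if it has lasted more.

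**Link to the primary endpoint.** A Grade 3 return before Week 48 that leads to discontinuation is a non-responder. The same return handled by a reduced dose can still be a responder. With 156 patients planned, one patient counted the other way moves the rate by 1/156 = 0.64 percentage points, and only if that patient would be in MMR at Week 48 on continued treatment. The documents do not say how many patients would have this sequence.

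**The case against.** The strongest reply is that the table is workable as written. Its first column is headed by worst toxicity and the footnote says the same, so a clinician would go to the row for the grade reached. At Grade 4 the Mandatory label supports this, and I accept it as the likely reading there. At Grade 3 it remains an inference against a sentence that names grade 2 and above.

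Three stronger readings are tempting, and the documents do not support them.

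- *That the bilirubin row contradicts itself.* It does not. Each state has at most one action, and a value that resolves within 14 days brings no dose cut.
- *That a patient with persistent bilirubin stays on full dose indefinitely without protection.* The row is a recommendation and liver tests continue until resolution. A rise above 3.0 x ULN, or a combined rise with AST/ALT that meets the table's thresholds, moves the patient to a mandatory row. (Above 3.0 x ULN, a note allows investigator discretion for a purely indirect rise without hemolysis.) Section 9.1.1 also requires stopping if continuation would harm the participant. What remains is a missing instruction within this range.
- *That the effect on the MMR rate can be sized from the diarrhea frequency reported at 200 mg q.d. in Section 4.2.* That figure is any-grade diarrhea in 12 phase I patients, including accelerated phase, at a dose this trial does not use before Week 60. It says nothing about recurrence at Grade 3 before Week 48.

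**Conclusion.** The point holds as two reconciliations of unequal weight.

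The diarrhea rows give two incompatible instructions for a Grade 3 return after a resolved Grade 2 episode. The overlap with Grade 4 exists in the wording but is arguably settled by the Mandatory label. The conflict lies between rows and arises only in that sequence. The Grade 3 row does not use the word permanently.

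The bilirubin row has a sequencing flaw and a gap: the reduction depends on late resolution, and continued elevation within the range is not addressed.

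The main ground is clarity of safety instructions. The primary endpoint is touched because discontinuation and dose reduction are handled differently before Week 48, but the effect is probably small. It needs a specific sequence of events in a patient who would otherwise be in MMR, and the documents give no frequency from which to calculate it. Sample size, power and alpha are unaffected. The conclusion rests on reading the rows literally, as sites would have to.

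**What to change.** At the next amendment, revise the wording of two rows of Table 6-4:

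- **Diarrhea:** reconcile the recurrence sentence in the Grade 2 row with the Grade 3 and Grade 4 rows, so that each grade at recurrence has one instruction.
- **Bilirubin above 1.5 and up to 3.0 x ULN, normal baseline:** reconcile the 14-day step with the instruction to maintain the dose, and make the row cover a value that stays in the range.

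Which clinical rule applies in each case is the sponsor's decision. The cost is the wording of two rows, in a table that Amendment 01 already revised, plus the usual notification of sites. No change to the SAP is needed.

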6. Eastern Cooperative Oncology Group (ECOG) performance status (PS) of 0, 1, or 2
7. Adequate end organ function as defined by:
- Total bilirubin $\leq 3 \times$ ULN; patients with Gilbert's syndrome may only be included if Total bilirubin $\leq 3 \times$ ULN or direct bilirubin ≤ 1.5 ULN
 - Serum lipase $\leq 1.5 \times$ ULN. For serum lipase $> \text{ULN} - \leq 1.5 \times \text{ULN}$, value must be considered not clinically significant and not associated with risk factors for acute pancreatitis
 - Alkaline phosphatase $\leq 2.5 \times$ ULN
 - Creatinine clearance ≥ 30 mL/min as calculated using Cockcroft-Gault formula
8. Patients must have the following electrolyte values within normal limits or corrected to be within normal limits with supplements prior to first dose of study medication:
- Potassium (potassium increase of up to 6.0 mmol/L is acceptable at study entry if associated with creatinine clearance* within normal limits)
 - Total calcium (corrected for serum albumin); (calcium increase of up to 12.5 mg/dl or 3.1 mmol/L is acceptable at study entry if associated with creatinine clearance* within normal limits)
 - Magnesium, with the exception of magnesium increase $> \text{ULN} - 3.0$ mg/dL; $> \text{ULN} - 1.23$ mmol/L associated with creatinine clearance* within normal limits
- *calculated using Cockcroft-Gault formula
9. Evidence of typical BCR-ABL1 transcripts [e14a2 and/or e13a2] at the time of screening which are amenable to standardized RQ-PCR quantification

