
Dose modifications for asciminib Please note that if a patient requires a dose interruption of > 28 days for any toxicity, and > 42 days for hematologic toxicity, then the patient should be discontinued from study treatment
	

Worst toxicity CTCAE Version 5.0
	
Asciminib

For patients with normal baseline ALT and AST and total bilirubin value:
 
AST or ALT > 3.0 x ULN combined with total bilirubin > 2.0 x ULN without evidence of cholestasis^d
 
For patients with elevated baseline AST or ALT or total bilirubin value [AST or ALT > 3 x baseline OR [AST or ALT > 8.0 x ULN], whichever is lower combined with total bilirubin > 2 x baseline AND > 2.0 x ULN
 
Note: For participants with Gilbert's syndrome, at least 2-fold increase in direct bilirubin
	
Mandatory: Hold dose
 
Repeat liver tests as soon as possible, preferably within 48 hours from awareness of the abnormal results, then with weekly monitoring of LFTs^b, or more frequently if clinically indicated, until AST, ALT, or bilirubin have resolved to baseline or stabilization over 4 weeks. Please refer to Section 6.6.4.1 for additional follow-up evaluations as applicable.
 
If DILI confirmed: permanently discontinue patient from study drug treatment
 
If not DILI – interrupt treatment. Treat identified cause according to institutional guidelines. If resolved, then reduce dose ↓ 1 dose level, if cause is treatment related.

Investigation (metabolic)
	

Amylase and/or lipase elevation
	

Grade 1: > ULN - 1.5 x ULN
	
Recommendation: Maintain dose level, measure 2x per week

Grade 2: > 1.5 - 2.0 x ULN; >2.0 - 5.0 x ULN and asymptomatic
	
Recommendation: Maintain dose level, measure 2x per week

Grade 3: > 2.0 - 5.0 x ULN with signs or symptoms; >5.0 x ULN and asymptomatic
	
Mandatory: Hold dose until resolved to Grade ≤ 1 or baseline, then: If resolved in ≤ 7 days, then reduce dose ↓ 1 dose level If resolved in > 7 days, then discontinue treatment and obtain appropriate imaging (i.e., MRI, CT scan, or ultrasound) **

Grade 4: > 5.0 x ULN and with signs or symptoms
	
Mandatory: Permanently discontinue patient from treatment. Obtain appropriate imaging (i.e., MRI, CT scan, or ultrasound) **

Vascular disorders
	

Hypertension
	

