
^d “Cholestasis” defined as ALP elevation (> 2.0 x ULN and R value < 2) in patients
 
Note: The R value is calculated by dividing the ALT by the ALP, using multiples of the ULN for both values. It denotes whether the relative pattern of ALT and/or ALP elevation is due to cholestatic (R ≤ 2), hepatocellular (R ≥ 5), or mixed (R >2 and < 5) liver injury.
 
* Note: If total bilirubin > 3.0 x ULN is due to the indirect (non-conjugated) component only, and hemolysis as the etiology has been ruled out as per institutional guidelines (e.g., review of peripheral blood smear and haptoglobin determination), then ↓ 1 dose level and continue treatment at the discretion of the investigator.
 
** Note: A CT scan or other imaging study to assess the pancreas, liver, and gallbladder should be performed within 1 week of the first occurrence of any grade ≥ 3 amylase and/or lipase elevation. If asymptomatic grade 3 elevations of lipase and/or amylase occur again at the reduced dose, patients will be discontinued permanently from study treatment. If asymptomatic grade 2 re-occur at reduce dose, closed monitoring of lipase and amylase will be required.
 
*** Note: Antidiarrheal medication is recommended at the first sign of abdominal cramping, loose stools, or overt diarrhea.
 
**** Note: An isolated bilirubin elevation is not typical for drug-induced liver injury. Bilirubin can be elevated either as part of a “Hy’s law” constellation with a preceding elevation of ALT/AST, or as part of a cholestatic reaction with simultaneous elevation of other cholestatic parameters (ALP, GGT). Isolated bilirubin can be seen in conjunction with drugs that inhibit bilirubin conjugation or excretion, but both scenarios do not typically represent liver injury. Alternative causes of bilirubin elevation should therefore, be ruled out before basing dose modification decisions on bilirubin values alone.
	

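### For a patient with Gilbert's syndrome, inclusion criterion 7 can be read to allow entry with total bilirubin above 3 x ULN, a level at which Table 6-4 changes the dose whatever the baseline

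*Protocol*

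**What the plan says.** **Entry (Protocol Section 5.1, criterion 7).** The bilirubin item opens with a limit of 3 x ULN on total bilirubin. A clause for Gilbert's syndrome follows: "patients with Gilbert's syndrome may only be included if Total bilirubin" meets that same limit, with an alternative after it, "ULN or direct bilirubin ≤ 1.5 ULN". The alternative puts no ceiling on total bilirubin.

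**On treatment (Protocol Section 6.6.3, Table 6-4, isolated total bilirubin elevation).**
- The row "> 3.0 - 10.0 x ULN (irrespective of the baseline levels") carries the instruction "Mandatory: Hold dose. Repeat LFTs within 48-72 hours then monitor LFTs" weekly until the value is at or below 1.5 x ULN or back at baseline. If that takes 14 days or less, the dose goes down one level. If it takes longer, the patient is discontinued.
- The row above 10 x ULN likewise applies "irrespective of the baseline levels". It sends the reader to footnote **** and otherwise discontinues treatment.
- Footnote *, attached to both rows, covers a value above 3 x ULN that is purely indirect, with haemolysis excluded. The action is to go down one "dose level and continue treatment at the discretion of the investigator".
- Footnote **** asks that other causes be excluded before bilirubin alone drives a dose decision. Only the row above 10 x ULN refers to it.
- The one provision in the table for Gilbert's syndrome is in the combined transaminase and bilirubin row: "syndrome, at least 2-fold increase in direct bilirubin".

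The text of Section 6.6.3 adds that sites may not deviate from mandatory interruptions or reductions.

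**The concern.** The entry rule and the dose-modification rule use the same threshold of 3 x ULN on total bilirubin, but they treat a high baseline differently. Criterion 7 appears to recognise that total bilirubin in Gilbert's syndrome may be high while direct bilirubin is not. The two upper isolated-bilirubin rows expressly ignore the baseline.

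If both are applied as written, a patient can be eligible and still meet a dose-change trigger at the first on-treatment chemistry sample, with nothing changed since screening. Table 6-4 handles this elsewhere: AST and ALT have a separate block for values elevated at baseline, and the combined row has its Gilbert's provision. The isolated-bilirubin rows have neither.

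At stake are consistent handling across sites and the justification for a dose change made without a new finding.

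**Working it through.** The plan states no figure on this point, and nothing here depends on alpha, power, effect size or sample size. The check is a comparison of thresholds.

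**Illustrative patient (assumed values):** Gilbert's syndrome, total bilirubin 3.5 x ULN, direct bilirubin 1.0 x ULN, stable.

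1. *Criterion 7, first branch:* 3.5 ≤ 3 is false.
2. *Criterion 7, alternative branch:* 1.0 ≤ 1.5 is true. The branches are joined by an or, so the clause admits the patient.
3. *Alternative reading of criterion 7:* if the opening limit of 3 x ULN binds every patient, this patient is excluded. The Gilbert's clause then admits nobody whom the opening limit would not, and its direct-bilirubin branch has no effect.
4. *Table 6-4 trigger:* Table 8-1 schedules chemistry at Week 2. An unchanged 3.5 x ULN lies above 3 and at or below 10 x ULN, and baseline is disregarded, so the mandatory hold applies.
5. *Recovery target:* 1.5 x ULN or baseline. The unchanged value equals baseline, so the target is met at once. This falls within 14 days, and the row's next step is a one-level reduction.
6. *Footnote \*:* if the elevation is indirect only and haemolysis is excluded, the instruction is again one level down, with continuation left to the investigator.

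| Route | Result for an unchanged entry value |
|---|---|
| Row above 3 and up to 10 x ULN, as written | Hold, then one level down |
| Same row with footnote * | One level down, continuation at investigator discretion |
| Row above 10 x ULN | Discontinuation unless footnote **** applies |
| Combined row with the Gilbert's provision | Not reached without a transaminase elevation |

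Neither route open to the illustrative patient keeps the starting dose. The same holds for any such patient who enters above 3 and up to 10 x ULN. A patient who enters at or below 3 x ULN and stays there is not affected.

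**The case against.** **The entry clause is ambiguous.** Criterion 7 opens with a ceiling for everyone, and the Gilbert's clause is phrased restrictively. The amendment's summary of changes also describes the admitted population by the 3 x ULN ceiling. If that ceiling binds, no eligible patient meets the trigger at entry. This stands to the extent that one can say only that the criterion can be read to admit such a patient. It does not clear the text, because the direct-bilirubin branch would then be idle and would itself need correcting.

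**Table 6-4 is for adverse drug reactions.** Its title, its toxicity column and the opening of Section 6.6.3 all concern intolerance. Under Section 10.1.1, conditions present at consent are medical history, and a laboratory value is an adverse event only if it causes symptoms, is clinically significant or needs therapy. A stable value known before the first dose is arguably outside the table. This is a fair reading, but the explicit instruction to disregard baseline points the other way, and the protocol does not settle which prevails.

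**Footnote \*\*\*\* is worded as a general principle.** Excluding other causes first would fit Gilbert's syndrome. However, the row that catches a value above 3 and up to 10 x ULN does not refer to it.

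**Disregarding baseline may be a deliberate, cautious choice.** That is possible. It still has to be squared with an entry clause that appears to allow such a baseline.

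**Conclusion.** The inconsistency is in the current text, but it is small. Read literally, criterion 7 and Table 6-4 together let an eligible patient's dose be changed with bilirubin exactly where it was at entry.

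A reader might infer more: that such a patient must eventually stop, counts as a Week 48 non-responder, and so costs the primary rate 1/156 = 0.64 percentage points. The documents do not support this.
- The discontinuation rule in Section 6.6.3 requires a toxicity to recur after treatment is resumed at a lower dose. A value that never changed has not clearly recurred.
- Footnote * leaves continuation to the investigator, and the branch for recovery after more than 14 days is not reached when the baseline target is already met.
- Dose modification and interruption are handled by treatment policy (Protocol Section 12.4.3; SAP Section 2.5.3), so a reduction alone does not make a patient a non-responder.
- The 0.64 points also need the patient to be in the FAS, to stop before Week 48 and otherwise to have responded. At the design rate of 33%, the expected loss per such stop is 0.33 x 0.64 = 0.21 points.

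Discontinuation is therefore possible but not shown, and no effect on the primary endpoint is established. Sample size and power are untouched. That few patients, possibly none, are affected is an assumption: the documents do not say how many participants have Gilbert's syndrome or enter above 3 x ULN.

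**What to change.** In the next amendment, reconcile criterion 7, the two isolated-bilirubin rows above 3 x ULN, and footnotes * and ****. Together they should state consistently (a) whether a patient with Gilbert's syndrome and total bilirubin above 3 x ULN is eligible, and (b) how a value unchanged from baseline is handled on treatment. Which threshold or action is right is a clinical decision for the sponsor, and this review takes no view on it.

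The cost is about one clarifying sentence in criterion 7 or Table 6-4, with matching references in the rows and footnotes. No change to the statistical analysis is needed.
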